#### 5.11 Adverse event and Serious Adverse Events Reporting and Management

#### Definitions

An adverse event (AE) is any untoward medical occurrence associated with the use of a drug in humans, whether or not considered drug related. Adverse events occur after enrolment and are defined as not being present prior to enrolment.

Serious adverse events (SAEs) are a subset of adverse events that are life threatening, require a surgical or medical procedure to prevent disability or death, result in admission to hospital, prolongation of hospitalization or transfer to an ICU, or results in death. A SAE can also be an important medical event that may not result in death, be life-threatening, or require hospitalization, but may jeopardize the subject and may require medical or surgical intervention to prevent one of the outcomes listed in this definition. A SAE is also an event that results in a congenital anomaly or birth defect.

The pharmacology and risks of alteplase in patients with acute ischemic stroke are well known; in addition, there are multiple recent phase II and one recent phase III trial attesting to the safety of intravenous tenecteplase in patients with acute ischemic stroke. Of note, in particular is the Norwegian Tenecteplase Stroke Trial (NOR-TEST) trial. This Phase III trial randomized 1100 patients using standard thrombolysis eligibility criteria to test if intravenous tenecteplase (at a dose of 0.4 mg/kg body weight) was superior to standard dose alteplase. The dose of intravenous tenecteplase

used in the NORTEST trial was higher than that proposed in this trial (0.25 mg/kg body weight, maximum dose 25 mg) while the dose of intravenous alteplase was the same as in this trial. The table below lists SAEs noted in the NORTEST trial in patients administered intravenous alteplase or intravenous tenecteplase. There was no difference in incidence of SAEs up until day 90 or patients affected by at least one SAE up until day 7. The NORTEST trialists reported the following SAEs, namely, any intracerebral hemorrhage, symptomatic intracerebral hemorrhage, death, angioedema, recurrence of ischemic stroke, epistaxis, chest pain, gastrointestinal bleeding, other extracranial bleeding and readmission as possibly or probably related to drug administration (see Table below). There were no differences in any of these expected SAEs between patients administered intravenous tenecteplase.

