Based on data from the NORTEST phase III trial and other recent phase II trials in acute ischemic stroke patients and based on substantial literature attesting to the safety of intravenous tenecteplase in patients with acute myocardial infarction for over 15 years, unexpected serious adverse drug reactions or events are unlikely in the trial. (See Table below for a list of SAEs from the NORTEST trial and Appendix, Table 1 for a list of expected adverse drug reactions that have been well described associated with stroke thrombolysis). The natural history of acute stroke is such that high morbidity is expected (See Appendix Table 1). Since both thrombolytic agents have a biological half-life measured in hours, treatment-related morbidity and AEs will occur within a short interval after administration.

	Tenecteplase (n=549)	Alteplase (n=551)	p value
All SAEs to day 90	145 (26%)	141 (26%)	0.74
Patients with at least one SAE up to day 90	127 (23%)	120 (22%)	0.59
Patients with at least one SAE up to day 7	61 (11%)	56 (10%)	0-62*
Possibly or probably related to study drug	51 (9%)	53 (10%)	0.85*
Any ICH†	47 (9%)	50 (9%)	0-82*
Symptomatic ICH‡	15 (3%)	13 (2%)	0.70*
Death	15 (3%)	14 (3%)	0.84*
Angio-oedema	1(<1%)	2 (<1%)	1.00*
Recurrence of ischaemic stroke	9 (2%)	5 (<1%)	0-30*
Recurrence of transient ischaemic attack	1(<1%)	0	0-50*
Epistaxis	0	1(<1%)	1-0*
Chest pain	3 (<1%)	5 (<1%)	0.73*
Gastrointestinal bleeding	1 (<1%)	o	0-50*
Other extracranial bleeding	4 (<1%)	9 (2%)	0.26*
Readmission	14 (3%)	22 (4%)	0-24*
Patients with at least one SAE, days 8–90	74 (13%)	75 (14%)	0-95
Possibly or probably drug related	6 (1%)	8 (1%)	0.79*
ICHS	6 (1%)	7 (1%)	0.79*
Death	14 (3%)	12 (2%)	0-68*
Angio-oedema	0	0	NA
Recurrence of ischaemic stroke	4 (<1%)	6 (1%)	0.75*
Recurrence of transient ischaemic attack	4 (<1%)	1 (<1%)	0-21*
Epistaxis	0	0	NA
Chest pain	4 (<1%)	7 (1%)	0-55*
Gastrointestinal bleeding	2 (<1%)	0	0.25*
Other extracranial bleeding	1 (<1%)	4 (<1%)	0-37*
Readmission	63 (11%)	68 (12%)	0.71

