- 2. Data on SAEs occurring within the first 24 hours including SAEs of special interest for the study, namely, a) symptomatic intracerebral hemorrhage (post-acute stroke treatment defined as per QuICR and OPTIMISE registries) b) angioedema and c) peripheral bleeding requiring blood transfusion will be collected through the trial database.
- 3. AEs measured routinely by the QuICR and OPTIMISE registries (highlighted as \* or # above) will be collected from those registries.
- 4. Administrative data linkages will be used to collect data on other AEs. The Canadian Discharge Abstract Database (DAD) captures all hospital separations for all Canadian provinces and

territories, with the exception of the province of Quebec. Each hospital discharge record includes up to 25 diagnosis codes, recorded using the ICD coding system, along with other clinical and demographic information. In addition, each diagnosis field in the database has an accompanying single digit field for the diagnosis type that is recorded whenever a diagnosis is recorded. The diagnosis type codes are as follows: type M: most responsible diagnosis; type 1: preexisting conditions (comorbidities) that influence care, or the hospital stay; type 2: conditions that arose after admission and that may thus represent complications of care; and type 3: preexisting conditions (comorbidities) that do not influence care, or the hospital stay. Type 2 diagnosis type codes will be used primarily to identify any AEs. Other data elements as relevant (interventions offered during admission; Group 11 or Blood transfusion given; Group 17) will also be collected. It will therefore not be possible to classify seriousness when data are obtained through administrative data linkages. Details on the data elements collected through DAD in each province will be made available in the MOP. The nature of the specific data linkages will be different in different jurisdictions (Alberta vs. Ontario). Data will be queried and obtained at regular intervals through the duration of the trial from the above data sources.

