	A Kaplan-Meier survival distribution. Patients alive after 90/120 days were censored. Logistic mixed-effects regression model with treatment (Tenecteplase vs Alteplase) as exposure; age, sex, baseline stroke severity, and stroke onset-to-needle time as fixed effects, and site, and registry (QuiCR vs. OPTIMISE) as random effects.
Symptomatic intracerebral hemorrhage	Risk difference and the corresponding 95%CI
	Logistic mixed-effects regression model with
	treatment (Tenecteplase vs Alteplase) as
	exposure; age, sex, baseline stroke severity, and
	stroke onset-to-needle time as fixed effects, and site, and registry (QuiCR vs. OPTIMISE) as random effects.
Intracranial Hemorrhage on follow-up Imaging (Blinded)	Difference in proportion of ICH categories and the corresponding 95%Cl

Page **7** of **9** 

 
Parenchymal hemorrhage (hemorrhagic infarction type 1, hemorrhagic infarction type 2, parenchymal hematoma type 1, parenchymal hematoma type 2, remote hemorrhagic infarction type 1, remote hemorrhagic infarction type 2, remote parenchymal hematoma type 1, remote parenchymal hematoma type 1, remote parenchymal hematoma type 2)
 
Subdural hemorrhage
 
Subarachnoid hemorrhage
 
Intraventricular
 
	
Peripheral Bleeding requiring Blood Transfusion	Risk difference and the corresponding 95%CI
Angioedema	Risk difference and the corresponding 95%Cl
Proportion of patients receiving EVT	Risk difference and the corresponding 95%CI.
	Logistic mixed-effects regression model with
	treatment (Tenecteplase vs Alteplase) as
	exposure; age, sex, baseline stroke severity, and
	stroke onset-to-needle time as fixed effects, and site, and registry (QuiCR vs. OPTIMISE) as random effects.
Other SAEs and SUSARs	Risk difference and the corresponding 95%CI

Page **8** of **9** 

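### Searching linked hospital records mainly for Type 2 codes leaves the cause of a readmission unidentified as an adverse event, although admission is itself a seriousness criterion

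*Combined protocol and SAP*

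**What the plan says.** Protocol Section 5.11 collects safety data by several routes.

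- **Trial database.** SAEs in the first 24 hours (Section 5.11, step 2; Section 7.2). Section 5.10 also sends death and symptomatic ICH there, as safety outcomes.
- **Registries.** A fixed list of events during the hospital stay (Section 5.11, step 3 and the list before it).
- **Linked administrative data.** All other AEs, from the Discharge Abstract Database (step 4). The rule is "Type 2 diagnosis type codes will be used primarily to identify any AEs". Intervention and transfusion fields are also collected, and provincial details are left to the manual of procedures.
- **Investigators.** A continuing duty to report serious unexpected drug reactions (step 5).

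Step 4 describes the coding: "Each hospital discharge record includes up to 25 diagnosis codes", and each diagnosis carries a type. The two types that matter here are "type M: most responsible diagnosis" and "type 2: conditions that arose after admission and that may thus represent complications of care". On seriousness, step 4 says: "It will therefore not be possible to classify seriousness when data are obtained through administrative data linkages".

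The definitions at the start of Section 5.11 count as serious those events that "result in admission to hospital, prolongation of hospitalization or transfer to an ICU, or results in death". The outcome table in SAP Section 9 has a row for "Other SAEs and SUSARs", analysed as a risk difference, with no stated source or time window.

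**The concern.** The type code belongs to a particular discharge record, so a Type 2 condition is one that arose after that record's own admission. An event at home that sends the patient back to hospital arose before the second admission. Its natural place on the new record is the most responsible diagnosis, which the stated rule does not search. The rule suits complications of the index stay. It does not suit events that cause a later stay, and these are serious by the protocol's own definition.

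The seriousness sentence adds to the problem. A database of hospital separations cannot support every seriousness criterion, but a new record is direct evidence on the admission criterion.

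At stake is the between-arm description of non-fatal events after discharge. The DSMC is to look at overall safety data for patterns not visible in single cases, and the SAP plans a comparison of other SAEs. Neither document says how a readmission and its cause would enter either one. The primary endpoint is not affected.

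**Working it through.** **Step 1. Which route would identify a non-fatal event that starts at home after index discharge and leads to readmission?**

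- Trial database SAE form: no, after 24 hours. Death and symptomatic ICH are the exceptions.
- Registry lists: no, because they cover the hospital stay.
- Investigator reports: only if the event is a suspected serious unexpected drug reaction.
- Discharge database, Type 2: not for the causing condition, which arose before that admission. A further complication arising during the readmission would be Type 2.
- Discharge database, intervention and transfusion fields: these may show that something was done. They do not give the presenting diagnosis.
- Home time (Section 5.10; SAP Section 9): counts time in the first 90 days when the patient is not an inpatient, so it registers readmission days but not their cause.

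No stated rule takes the Type M diagnosis from a later record.

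**Step 2. Check the benchmark table.** Section 5.11 reproduces SAE counts from the cited phase III trial (549 tenecteplase, 551 alteplase). For readmission in days 8-90:

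- 63/549 = 11.5% and 68/551 = 12.3%, printed as 11% and 12%.
- Fisher exact p = 0.710, printed as 0.71.

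The p-value fits a reading in which the row counts patients but does not prove it, since the table's first row counts all SAEs.

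**Step 3. Size of the class.** The denominator is the row "Patients with at least one SAE, days 8–90": 74 + 75 = 149.

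- Readmissions: 63 + 68 = 131, and 131/1100 = 11.9%.
- Share of patients with a late SAE: 131/149 = 87.9% (63/74 = 85.1% tenecteplase; 68/75 = 90.7% alteplase).

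**Step 4. Worst-case lower bound.** The item rows overlap: they sum to 98 and 105 against 74 and 75 patients. Suppose every death, ICH, recurrent stroke and bleed in days 8-90 is caught by another route, and each fell in a different readmitted patient.

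| Removed in turn | Count | Remaining | Share of 149 |
|---|---|---|---|
| Deaths | 14 + 12 = 26 | 105 | 70.5% |
| ICH | 6 + 7 = 13 | 92 | 61.7% |
| Recurrent ischaemic strokes | 4 + 6 = 10 | 82 | 55.0% |
| GI and other extracranial bleeds | 2 + 5 = 7 | 75 | 50.3% |

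This is generous to the plan, because the registry route for recurrent stroke covers only the hospital stay.

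**Step 5. How much of this was thought drug related?** In days 8-90, 6 + 8 = 14 patients had SAEs judged possibly or probably related: 14/1100 = 1.3%.

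**Step 6. Scaling to 1600 patients, if the rates carried over (an assumption).** Readmissions: 1600 × 131/1100 ≈ 191. Worst-case bound: 1600 × 75/1100 ≈ 109. Possibly or probably related: 1600 × 14/1100 ≈ 20.

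**The case against.** The case for leaving the text alone has real strength.

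- **The rule is not exclusive.** It says primarily, and it defers the data elements to a manual that is not among the documents. That manual may already screen Type M. This stands, and it limits the finding to what Section 5.11 states. But the only extra fields named do not give the cause of a readmission, and the main identification rule belongs in the protocol or SAP.
- **Late events are treated as unrelated to the drug.** Section 5.11, step 1, says so because both half-lives are short, and the 14 related cases point the same way. This lowers the stakes. The plan still collects late AEs, and a comparison between arms does not rely on case-by-case attribution.
- **Linked data may not feed the SAP row at all.** If seriousness cannot be classified, the row would draw on trial-database SAEs and investigator reports, and Type 2 selection would not distort it. This is a fair reading. What it leaves is a row whose sources and window are unstated.

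A reader might go further and infer that a drug causing more readmissions would look as safe as its comparator. The documents do not support that: home time is compared by arm, and extra inpatient days would reduce it. A reader might also infer that safety observation ends at index discharge. It does not: the database captures all separations outside Quebec, data are to be obtained at regular intervals throughout the trial, and nothing restricts the search to the index record.

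**Conclusion.** The point holds in a limited form. As Section 5.11, step 4, is written, the diagnosis that causes a readmission is not identified as an AE, and the statement on seriousness sits badly with the protocol's own admission criterion. The gap covers non-fatal events leading to readmission after index discharge.

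The benchmark suggests this class is a large part of late serious events: 88% of patients with an SAE in days 8-90 if rows count patients, and at least 50% in the worst case. These figures show scale and are not a forecast. They are all-cause, come from a trial with a different tenecteplase dose (0.4 mg/kg) and milder strokes, and days 8-90 only approximates the time after discharge. It would be wrong to read the 191 as missed drug harms; the same table gives about 20 on the possibly or probably related count.

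Confidence is medium, because the manual could already close the gap. The change is worth making for the safety comparison, and lies between advisable and worth considering.

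**What to change.** **Protocol Section 5.11, step 4.**

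- Use Type 2 codes on the index episode, with inter-hospital transfers treated as part of that episode.
- On every separation with an admission date after index discharge and within 90 days of randomisation, take the Type M diagnosis as the AE term and also extract Types 1 and 2.
- Report all-cause readmissions by arm, tabulated by Type M diagnosis. Separate planned admissions only if the linked data allow it, since the protocol names no field for this.
- Replace the seriousness sentence with: admission- and death-based seriousness is derived from the record; other criteria are not available.

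**SAP Section 9.** State the sources and time window of the row for other SAEs. Show 24-hour trial-database SAEs separately from linked readmission-based SAEs to day 90. Restrict the linked rows to patients in provinces covered by the database, since step 4 places Quebec outside it.

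**Cost.** Protocol and SAP wording, and a wider query on records already being linked; no new data collection from patients. Unrelated and some planned readmissions will be counted, by the same rule in both arms, so the reported rate will be higher. Provincial differences in linkage will still need handling in the manual.

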# 6. Statistics

#### 6.1 The proposed sample size and justification

The primary endpoint is the proportion of subjects that achieve a 90-day score of 0 or 1 on the mRS scale in both arms. The choice of this dichotomous outcome is based on clinical acceptance, an assessment of the distribution of mRS in the individual patient level meta-analysis and the choice of similar outcome in most ongoing trials.

A total of 1600 subjects will be randomly assigned to receive either intravenous tenecteplase or alteplase in a 1:1 ratio. Based on prior literature, we assume that the incidence of primary outcome (mRS 0-1) 90 days after randomization will be 38% and 35% respectively. Assuming a one-side non-inferiority margin of 5%, a one-sided significance Type I error of 2.5% and 90% power to show that tenecteplase is non-inferior to alteplase, we will need 759 subjects in each arm of the trial. The choice of 5% as a non-inferiority margin represents 50% of the estimate of effect size (10%) for intravenous alteplase administered within 3 hours of stroke symptom onset vs. control for the outcome mRS 0-1 measured at 90 days. This data from Emberson et al is the largest patient level

Version 2.0

26

pooling of data from all intravenous alteplase vs. control trials to date. The choice of 5% as the noninferiority margin in this trial means that at least half of the point estimate of effect for intravenous alteplase vs. control will be preserved. Additionally, the choice of 5% is strictly less than the lower CI bound of ~6% on the same point estimate in data from Emberson et al. Hence the non-inferiority margin is guaranteed to be less than the lowest reasonable estimate of alteplase vs. control (placebo) effect size.

As always with non-inferiority designs, the 5% non-inferiority margin is the lower boundary on the 95% confidence interval surrounding the point estimate obtained from the proposed trial. As a specific example, if the rate of excellent functional outcome in the alteplase group is actually 35% as postulated, the worst corresponding rate in the tNK group which will meet the non-inferiority test is 34.7%, for which the lower confidence bound on the difference is - 4.96%. In the ESCAPE trial that we led, loss to follow-up for primary outcome was 1.3%. Similar rates are seen in the ongoing trials that we lead (ESCAPE NA 1 and TEMPO 2 trials; approximately 2 to 4%). We therefore estimate a loss to follow-up rate <5%, thus resulting in a sample size of 1600 subjects.

Missing data rate in the QuICR registry in 2017 was < 5% for all data fields. The OPTIMISE registry is achieving similar metrics in 2018. Data linkages with administrative data sources and central telephone assessment of primary outcome by trial personnel in co-ordination with registry personnel will also ensure that loss to follow-up is minimal.

#### 6.2 The planned recruitment rate

Data from the QuICR registry (years 2016 - 2018) suggests that 550 to 600 patients with acute ischemic stroke receive thrombolysis every year within Alberta. The proposed trial has pragmatic eligibility criteria; any patient who is eligible for thrombolysis as per current guidelines and treating physician discretion is eligible for recruitment into the trial. Trial recruitment will use the existing registry infrastructure and processes to recruit subjects into the trial. Quick and easy randomization will be readily available to frontline physicians and allied health personnel at the emergency room. Information about the trial will be repeatedly reinforced as part of the QuiCR and OPTIMISE registries' ongoing quality improvement collaborative (see attached letters of support from both registries). Although ideally, we would like to enroll every eligible patient in the trial, after accounting for other ongoing acute stroke trials and being pragmatic about potential difficulties in trial enrolment early on, we will target at least 50% of all current thrombolysis eligible patients for recruitment in the first year at each enrolling site. This would mean approximately 300 subjects recruited in the first year into the trial from sites participating in the QuICR. OPTIMISE sites will also be participating. These sites average over 1200 thrombolysis cases per year in total, so again if conservatively, only 50% of all current thrombolysis eligible patients are recruited in the first year, this would mean 600 patients per year once all sites are running. Even if only half the sites in both registries are actively enrolling in the first year, this would still allow us to recruit at least 450 patients in the first year and 600 or more patients from year two onwards. Between the QuICR and OPTIMISE sites therefore, even accounting for variability in site initiation, contracts and REB approvals, we expect to be able to complete enrollment in 3 years.

#### 6.3 Participant Compliance Monitoring

Because the treatment is a one-time dose of an intravenous thrombolytic agent, given immediately after randomization, no problems with compliance are anticipated in the trial.

#### 6.4 Rate of loss to follow up and Missing data

We are estimating a loss to follow up rate of < 5%. Central assessment of primary outcome by trial personnel in co-ordination with registry personnel will ensure that loss to follow-up is minimal. In the ESCAPE trial, loss to follow-up was 1.3%. Similar rates are seen in the ongoing trials that we lead (ESCAPE NA 1 and TEMPO 2). Sensitivity analyses using various imputation techniques (worst case, best case, multiple imputation, hot-decking and nearest neighbor) will be specified prospectively in the Statistical Analysis Plan (SAP) if more than 5% of patients randomized are missing the primary endpoint.

#### 6.5 Centers involved

The QuiCR registry currently includes 15 Primary Stroke Centers that provide thrombolysis treatment only, and 2 Comprehensive Stroke Centers that provide both thrombolysis treatment and endovascular treatment. OPTIMISE registry sites will also be participating. All QuICR and OPTIMISE sites, as well as additional sites, will be eligible to participate in this study if they a) are actively participating or agree to participate in one of the two registries or b) have regular institutional reporting/contribution of data to administrative datasets (e.g. Discharge Abstract Database) that can be accessed and linked to trial outcomes as per statistical analysis plan, and c) obtain local REB/IRB approval.

